10.2 OUTLINE OF STUDY PROCEDURES AND ASSESSMENTS

All post-baseline visits should take place at the end of the defined period (i.e. Month 1 visit should be scheduled at the end of Month 1, Month 2 visit should be scheduled at the end of Month 2, etc.). One month is defined as 28 days/4 weeks. Post-baseline visit dates are calculated from Day 1 visit date :

- Month 1 (Day 29), Month 2 (Day 57), Month 3 (Day 85), Month 4 (Day 113), Month 5 (Day 141) and Month 6 (Day 169) for the Treatment Period,
- Month 1 FU (Day 197), Month 2 FU (Day 225), Month 3 FU (Day 253), Month 4 FU (Day 281), Month 5 FU (Day 309) and Month 6 FU (Day 337) for the Follow-up Period.

A window of ± 3 days is allowed for each visit scheduled during the treatment period. A window of ± 7 days/1 week is allowed for each visit scheduled during the follow-up period. The visit schedule is illustrated in Figure 2 below:

* Subjects who discontinue treatment prior to Month 3 will not enter the follow-up period.

** At the end of the 6-month follow-up, subjects with a BMD decrease from baseline of $> 1.5\%$ for lumbar spine and/or $> 2.5\%$ for total hip will have an additional DXA scan 6 months later.

Figure 2 : Schedule of Visits

The timing of events is shown in the Schedule of Assessments (Appendix A and Appendix B).

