The subject will take her first dose of study medication at the study site. The exact time of dosing (hour/minute) will be recorded in eCRF.

After drug administration, the following procedures will be performed:

- ECG at about the same time as but before the post-dose PK sample
- Post-dose PK sample taken at least 1.5 h after treatment administration. The exact time of dosing and of PK sampling (hour/minute) will be recorded in the eCRF.
- Contraception dispensing (if applicable) and counselling

The subject will receive double barrier contraception (condoms with spermicide) if requested. If the subject is at risk for acquiring HIV, she will be instructed to use double non-hormonal barrier contraception without spermicides (condoms and diaphragms).

Upon completion of the visit, the subject will be provided with emergency contact phone numbers and will be scheduled for her next visits.

For the whole duration of the treatment period, the subject will take her daily dose of study medication at home except on the day of study visits where she will take her daily dose at site.

10.2.2.2 Study visits: Month 1 (Day 29 -3/+2 days) and Month 2 (Day 57 ± 3 days)

The following tests and evaluations will be performed :

- eDiary completion compliance check
- ePRO and ClinRO completion, ideally before any other procedures or assessments:
 - at Month 1 visit: EHP-30, HRPQ, HRUQ, PROMIS, EQ-5D-5L, mPGIS, PGIC
 - at Month 2 visit: HRPQ, HRUQ, mPGIS, PGIC

with mPGIS and PGIC completed last.

- Concomitant treatments recording
- AE recording
- Completion of the paper C-SSRS questionnaire (version for “already enrolled subjects” (see Appendix S) for patients responding to the C-SSRS for the first time during the study, or version “since last study visit” (see Appendix T) for patients for whom the C-SSRS was completed at the previous study visit)
- IMP accountability based on blisters
- ECG (at about the same time as but before the PK sample)
- Vital signs (BP and heart rate)
- Urine pregnancy test
- Urinary protein dipstick
- Blood samples for haematology, coagulation parameters, chemistry, lipids, hormones (overnight fasting required at Month 1 visit only)
- Pre-dose PK sample (the time of study medication administration on previous 4 days and time of PK sampling will be recorded)
- Contraception dispensing (if applicable) and counselling
- Dispensing via IWRS of one new kit of linzagolix/placebo

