4.2.9. Visit Windows

For all analyses except for the DXA assessments and the diary questionnaires, the visits as collected in the eCRF will be used.

E-diary questionnaires:

For diary questionnaires (EHP-30, EQ-5D-5L, HRPQ, HRUQ, PGIC, PPGIC, PGIS, PROMIS, SSIQ) except for the PSIQ, the e-diary dates of assessment of each visit will be checked versus the dates of same visit in eCRF to handle for e-diary visit errors. Only assessments within the window of the date of eCRF+/-14 days will be used in analyses. For Day 1 assessments, only data prior to the first dose will be used, regardless of the questionnaire visit name. In case of multiple assessments falling within the same window of an eCRF date, the non-empty record with completion date closest to the eCRF date will be used.

For data from discontinued visits, the discontinuation visit date should be compared to theoretical visit dates. Only assessments within the window of theoretical date +/-14 days will be used for analyses, if it is planned to have a such assessment at this visit and no other assessment is in the window. If a subject discontinued in the main treatment period, date will be compared to the theoretical visit dates in main treatment period as described in Table 3. If a subject discontinued in the follow-up period, date will be compared to the theoretical visit dates from Table 4. Note that assessments from

Sponsor:	ObsEva		
Protocol:	18-OBE2109-003		
Document Version No.:	V5.0		

discontinued visits in **Exercise** eDiary device are entered under Month 6 (Month 6 FU in follow-up). They will be recoded as discontinued visits before applying the windowing rules.

Table 3 Theoretical Visit Dates in Main Treatment Period

Visit	Theoretical Date
Month 1	Day 29
Month 2	Day 57
Month 3	Day 85
Month 4	Day 113
Month 5	Day 141
Month 6	Day 169

Table 4 Theoretical Visit Dates in Follow-up

Visit	Theoretical Date
Month 1 FU	Month 6 date or treatment discontinuation date + 28
Month 2 FU	Month 6 date or treatment discontinuation date + 56
Month 3 FU	Month 6 date or treatment discontinuation date + 84
Month 4 FU	Month 6 date or treatment discontinuation date + 112
Month 5 FU	Month 6 date or treatment discontinuation date + 140
Month 6 FU	Month 6 date or treatment discontinuation date + 168

Pharmacokinetics data:

Visit windows rules for PK data will be the following:

CRS-BS-TP-000005 V 1.0

Page 47 of 127

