4.2.11. Last treatment administration date, End of Study date and Period definitions

The last treatment administration date will be defined as the date from the treatment termination of main period eCRF page. If this date is missing, the last date with a drug intake in eDiary strictly inferior to Month 6 date or the last date with a drug intake in eDiary available if the subject discontinued will be used.

For each 28-day period prior to Month X (except Month 6), the end of the period will be defined as the Month X visit date. If subject discontinued prior to Month X, the end of the period will be the date from the treatment termination of main period eCRF page or the last date with a drug intake in the eDiary if missing. If the subject missed the Month X visit (but did not discontinued), the subject might still have filled the diary during that time: the theoretical Month X date will be used to define the end of the 28-day period. The theoretical Month X is defined with respect to Day 1 as Month X= Day 1+ 28*X. Theoretical visits are presented in Table 3 of Section 4.2.9.

For the 28-day period prior to Month 6, the end of the period will be defined as the last treatment administration date.

The end of study date will be Month 6 date -1 day for subjects entering the Extension, and the last assessment date defined as last eCRF (excluding AE and CM end dates) or eDiary date in main study or main Follow-up for subjects not entering the Extension. This will not necessarily be the same date as last assessment date as recorded in the eCRF.

Note: For summaries by visit (efficacy or safety), the Month 6 assessments will be included in the main study analyses. For Adverse Events, Concomitant Medications and Daily diaries, data collected on Month 6 date will be part of the extension for subjects entering the extension study, and be part of the Follow-up period for subjects entering the main study follow-up period.

The main treatment period will be defined as Day 1 up to (Month 6 date -1) or treatment discontinuation date.

The main follow-up period will be defined as the Month 6 date or (treatment discontinuation date+1) up to the end of study date (for subjects who entered the follow-up).

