4.6.4. Additional Secondary Endpoints

All additional efficacy endpoints will be summarized by descriptive statistics for each treatment group, for each time point, including summaries of change from baseline when applicable. Individual linzagolix versus placebo treatment group comparisons will be made.

In general, between group comparisons for continuous endpoints will be analyzed via analysis of (co)variance. Between-group comparisons for binary endpoints will be analyzed via logistic regression. Between-group comparisons for ordinal categorical data will be analyzed using a Mantel-Haenszel test, or using Koch's method when there is also a baseline covariate.

As described in section 4.2.5 additional secondary endpoints will use Bonferroni correction for p-values of comparison of treatment groups at each visit. The analyses do not form part of the fixed-sequence strategy being used for the ranked secondary endpoints and will not be fully controlled for an overall type I error rate.

Values for all endpoints that are collected daily using the eDiary (from Section 4.6.4.1 to Section 4.6.4.18) will be based on the 28 calendar days immediately prior to and including the day of the corresponding visit or prior to and including the last treatment administration date for Month 6, or the 28 calendar days immediately prior to and including the last dose date for subjects who discontinue treatment prior to the visit in question (or fewer if treatment is stopped less than 4 weeks after first dose date), in order to estimate the treatment effect while under treatment. The last 28 days on treatment will be used at all subsequent scheduled visits for those discontinued subjects. Descriptive summaries for each 28-day period will be performed in two ways however:

- Once including only values of 28 days prior to Month X, i.e. using the last 28 days prior to Month X eCRF visit date for subjects who have not discontinued up to that month. If subjects discontinued prior to Month X the corresponding value will be missing from the summary at Month X;
- Once applying the while on treatment strategy, i.e. using the last 28 days prior to Month X eCRF visit date for subjects who have not discontinued up to that month, and for subjects who discontinued prior to Month X, the last 28 days prior to treatment discontinuation will be used. For all subsequent timepoints (Month X+1, etc.) the same last 28 days prior to treatment discontinuation will be used.

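### For women still on treatment with a Month 1 visit on Day 26 or 27, the 28-day diary window takes in two or one pre-dose days, which can supply anywhere from none to all of the Month 1 dysmenorrhea score

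*SAP*

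**What the plan says.** SAP 4.6.4 sets the window for every daily-diary endpoint at the scheduled visits: values "will be based on the 28 calendar days immediately prior to and including the day of the corresponding visit". SAP 4.2.11 adds that, for every month except Month 6, "the end of the period will be defined as the Month X visit date". SAP 4.2.9 says that, outside DXA and the visit questionnaires, "the visits as collected in the eCRF will be used". So the actual visit date counts; the theoretical date is used only if the visit was missed. These sections fix the end of the period and its length, but not a start relative to the first dose. The one shortening in 4.6.4 is for women who stop treatment less than four weeks after first dosing. The same paragraph gives the purpose as estimating the effect during treatment.

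Protocol 10.2.2.2 gives the visit as "Month 1 (Day 29 -3/+2 days", that is, Day 26 to Day 31. Protocol 10.2 states more generally: "A window of ± 3 days is allowed for each visit scheduled during the treatment period". The two differ only on the late side, so Day 26 is permitted under both. On Day 1, "The subject will take her first dose of study medication at the study site" (Protocol 10.2.2.1). Day 1 is to fall on the first to seventh day of menstruation, exceptionally on Day 8 to 12 of the cycle (Protocol 10.2.1).

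Under SAP 4.6.2.1.1, DYS is the mean over days with bleeding or spotting and is set to zero if there are none. Non-menstrual pelvic pain (NMPP) uses the other days. SAP 4.6.4.1 applies the same responder definition to visits other than Month 3.

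**The concern.** A window that is always 28 days long and ends on the actual visit can begin before treatment did. The plan guards against a short treatment period for women who discontinue, but not for women who continue and simply attend early. Pre-dose diary entries exist, because the diary is completed daily from screening.

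One or two days in 28 sounds trivial, but DYS is not a 28-day mean. Its denominator is the bleeding days, often only a few, and Day 1 is deliberately placed in or near menses. The excess days can therefore carry much more weight in DYS than in a 28-day average. The same days feed the bleeding-day analgesic component of DYS response, the counts of bleeding days and of moderate or severe pain days, and the mean worst pain score, where they could supply up to 2 of the 5 highest values. At stake is whether the earliest on-treatment comparison describes treated days only.

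**Working it through.** **Plan's own figure.** SAP 4.2.11: "The theoretical Month X is defined with respect to Day 1 as Month X= Day 1+ 28*X". With X = 1 this gives Day 29, matching SAP Table 3. The diary minimum also reproduces: 12/28 = 42.9%, stated as 43%.

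**Pre-dose days.** Number days consecutively with first dose = 1, so the day before is 0. A 28-day window ending on visit day v runs from v − 27 to v.

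| Visit day | Window starts | Pre-dose days | Share of 28 |
|---|---|---|---|
| 26 | −1 | 2 | 7.1% |
| 27 | 0 | 1 | 3.6% |
| 28 | 1 | 0 | 0% |
| 29 | 2 | 0 | 0% |

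If the wording were read as 28 days plus the visit day, the counts for Days 26, 27 and 28 would be 3, 2 and 1.

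**Share of the DYS mean.** Share = pre-dose bleeding days ÷ all bleeding days in the window. The documents do not give menses length, the distribution of Day 1 within the cycle, or bleeding on treatment, so these are assumptions.

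*Worked case.* Day 1 is on cycle day 4, menses last 6 days, and the visit is on Day 26. The two pre-dose days are cycle days 2 and 3. Study Days 1 to 3 are cycle days 4 to 6.
- No further menses in the window: 2/(2 + 3) = 2/5 = 40%.
- 28-day cycle: the next menses starts on study Day 26, adding one day: 2/6 = 33%.
- 21-day cycle: the next menses covers study Days 19 to 24, adding six days: 2/11 = 18%.
- For a Day 27 visit the three results are 1/4 = 25%, 1/6 = 17% and 1/10 = 10%.

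*Five-day menses, no further bleeding, by cycle day of Day 1.*

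| Visit | 1 | 2 | 3 | 4 | 5 | 6 | 7 |
|---|---|---|---|---|---|---|---|
| Day 26 | 0% | 20% | 40% | 50% | 67% | 100% | 100% |
| Day 27 | 0% | 20% | 25% | 33% | 50% | 100% | no bleeding |

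*Range over menses of 3 to 7 days and Day 1 on cycle day 1 to 7.* Cycle lengths of 21 and 38 days are half of the 42 to 76 days allowed for two cycles in inclusion criterion 8.

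| Later bleeding | Day 26 visit | Day 27 visit |
|---|---|---|
| None, or 38-day cycle | 0–100% | 0–100% |
| 28-day cycle | 0–67% | 0–33% |
| 21-day cycle | 0–40% | 0–25% |

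**The two ends of the range.** At 0%, with Day 1 on cycle day 1, the pre-dose days belong to the end of the previous cycle. They are normally non-bleeding, so they enter Month 1 NMPP and are usually also the last baseline days. At 100%, all bleeding in the window came before the first dose. The woman then gets a wholly pre-dose DYS score instead of the zero that the plan assigns when there is no bleeding.

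**The case against.** The strongest reply is that SAP 4.2.11 already defines the main treatment period as starting on Day 1 and 4.6.4 states an on-treatment aim, so a sensible programmer would drop earlier entries. That makes the gap one of wording, but it does not close it: neither sentence truncates the 28-day window, and the only stated exception is for women who stop. The sponsor has also treated a similar matter as needing explicit text. SAP section 5 removes the single Month 6 visit day because main-study treatment is not taken on it.

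Other objections stand and limit the point. A share of days is not a size of bias. In the worked case the remaining bleeding days are study Days 1 to 3 of the same menses, so removing the pre-dose days may move the mean little. The rule is the same in all arms. The analyses are outside the fixed sequence, and SAP 4.2.5 treats visit-wise response rates as primarily descriptive.

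A reader might infer that the pre-dose days are usually bleeding days, or that the Month 1 treatment difference is pulled toward zero by a material amount. The documents support neither. They do not say where in cycle days 1 to 7 Day 1 tends to fall, and the share is 0% when it is cycle day 1. Dilution is the plausible direction, because pre-dose days cannot reflect treatment, but nothing allows it to be sized.

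It is also fair that bounding the start is not a one-line change, because other SAP rules assume 28 days.

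**Conclusion.** The concern holds as a minor gap. As written, a Month 1 window ending on Day 26 contains two untreated days and one ending on Day 27 contains one; visits on Day 28 or later are unaffected. Within these women the pre-dose share of the DYS mean runs from 0% to 100%, and that range rests on assumed menses length, cycle day of Day 1 and later bleeding. How many women attended on those days is not stated, and the effect on scores, response rates or treatment differences cannot be computed from the documents.

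Only Month 1 additional secondary results are involved. It would be wrong to read this as touching the main conclusions: the Month 3 co-primary and Month 6 ranked windows end long after the first 28 days for women who stay on treatment, and women who stop early fall under separate rules.

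**What to change.** State in SAP 4.2.11 that the 28-day period starts no earlier than the first dose date: start = the later of Day 1 and visit day − 27. Then align the rules that assume 28 days:

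- **Averaged scores and DYS/NMPP response:** use the 26 or 27 available days.
- **Day-count endpoints:** use the actual number of on-treatment days as an offset, or scale to 28 days. The negative binomial code in 4.6.4.3 has no offset, so a shorter window would otherwise lower the counts mechanically.
- **Proportion of days intercourse was avoided (4.6.4.15):** replace the fixed 28 in the denominator with the actual number of days.
- **Non-responder rule (4.2.8.1 and 4.6.2.1.2):** say that women continuing treatment with an early Month 1 visit are not caught by the rule for under 28 days of treatment.

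Women whose only bleeding in the window was pre-dose would then score zero for DYS under the existing rule; the text should acknowledge this. If Month 1 tables already exist, count the affected women and re-run as a labelled sensitivity analysis.

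The cost is a small derivation change and one or two fewer days for the women concerned, still well above the 12-day minimum.
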